The data on the screening forms will be coded and retained in REDCap to allow investigators to monitor the number of persons screened and pass/failure rate.

During normal research operations (non COVID19), participants who meet inclusion/exclusion criteria as part of the phone screen will be scheduled for an in-person visit. During COVID19, research staff will continue with screening and consent process over the phone or through a

secure teleconference platform. Research staff will also make sure participants' Parkinson's medications are stable (had not had any changes or additions) for two weeks prior to their first in-person visit. Screened-in participants will be mailed, secure emailed, or handed a letter with information to help them prepare for their subsequent baseline assessment visit. This letter will also contain contact information for study personnel if questions arise.

In-Person Screening Process:

After consenting, potential participants will be screened in-person to determine if they meet all study inclusion / exclusion criteria. The elements included in the screening process are part of a routine Physical Therapy Evaluation.

Assessment Procedures:

Those subjects who meet inclusion criteria will participate in a baseline assessment session (approximately 3 hours in duration if fully done in person, approximately 45 mins - 1 hour if portions done remotely), followed by random allocation to one of two exercise conditions (each lasting 12 months in duration). Participants will be informed of their group assignment at the time of the baseline assessment or 1-2 business days after the assessment via phone. Participants will receive information about their group assignment and preparation for their initial visit by mail, secure email or in person. Both exercise conditions include up to 8 physical therapy intervention sessions (approximately 1 hour in duration), at 3 and 6 months, and end with participation in a final assessment session (approximately 3 hours in duration if done fully in person, approximately 1 hour if portions done remotely) occurring post intervention at 12 months.

Primary Outcome Measure:

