Physical Activity: Physical activity will be measured during a one-week period following each of the 4 assessment sessions using the StepWatch™ Activity Monitor (SAM). Subjects will wear the unobtrusive StepWatch 4 Activity Monitor (SAM, Modus Health, Edmonds, WA,), 24 hours per day for 7 days, except when bathing, showering, or swimming. The SAM is approximately the size of a pager, weighs 38g, and is attached using Velcro closures immediately proximal to the lateral malleolus of either leg. Study personnel will log pertinent setup information (start time, height, weight etc) on the SAM Setup form. The SAM is a small, waterproof, highly durable, self-contained device that is worn on the ankle and records the number of strides taken every minute. The SAM uses a combination of acceleration, position, and timing to detect steps taken with the leg of attachment. It is designed for long-term use during daily activities performed in an individual's customary environment over hours or days without maintenance by the user. Data are recorded as a temporal series of counts, with each data point represents the number of steps per one-minute interval. Step counts will be summed across days. In the rare event that the SAM device is returned after the 7 day wearing period and the data is unusable or the device has been damaged, the participant may be asked to wear an alternate SAM device for another 7 consecutive days.

The SAM will continuously monitor the number of steps taken over 7-days between the assessment period (after consent), but before the initiation of the intervention. The primary

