comparison will be to a 7-day period following the 12-month intervention period. The SAM does not provide feedback to the subjects regarding number of steps taken in order to reduce influence on behavior. The SAM has good validity and reliability in older adults and people with PD (Resnick, 2001). Step detection accuracy exceeds 98% both for unimpaired gait and for movement styles that have traditionally been difficult to monitor accurately such as Parkinsonian shuffling, hemiparetic gait, and dyskinetic gait (Cavanaugh, 2007; Speelman, 2011). The SAM is considered to be a more accurate method of assessing adherence to a walking program than alternative strategies such as exercise calendars, which can experience inaccurate recording (Gaines, 2005). The SAM can be setup remotely and mailed to the participant for use for 7 days at home. Devices will be returned to study staff through pre-paid boxes provided to participants and include pickup at their home.

At each assessment visit (whether in person or remote), subjects will be set up with the SAM and provided a handout with instructions about wearing the device and logging “non-wearing” time. After each assessment, subjects will be provided with a pre-paid box to return the device to study staff.

Secondary Outcome Measures: It is indicated next to each assessment, whether it can be done remotely, in person (research site or home) or both.

Motor Assessments

- Six-Minute Walk Test (6MWT) (In-person only)
- Ten-Meter Walk Test (10MWT) (In-person only)

Six-Minute Walk Test (6MWT): This is a measure of the distance a participant walks in a six-minute time period. The six-minute walk test is a safe, simple, and useful measure of walking ability in patients with Parkinson's disease. The test will be carried out on level, obstacle-free enclosed corridors. Each participant will be instructed to cover as much ground as possible on foot in six minutes. A tester will accompany the participant, acting as a timekeeper and guarding the participant as needed. This test takes about 10 minutes to administer. Greater distances indicate increased ability for community ambulation.

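### Participants can learn their arm before the baseline step-monitor week ends, so the baseline of both primary change scores is open to a reaction to the assignment

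*Protocol*

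**What the plan says.** **Disclosure.** Protocol, Assessment Procedures, has the baseline session "approximately 45 mins - 1 hour if portions done remotely), followed by random allocation to one of two exercise conditions", and then: "Participants will be informed of their group assignment at the time of the baseline assessment or 1-2 business days after the assessment via phone". In the SAP (Randomization and relevant demographics), the coordinator may randomise once eligibility is confirmed and consent obtained. Completed monitor wear is not a condition.

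**Baseline wear.** Protocol, Primary Outcome Measure: "Physical activity will be measured during a one-week period following each of the 4 assessment sessions". Wear lasts 7 days, and "At each assessment visit (whether in person or remote), subjects will be set up with the SAM". The same section allows other routes: "The SAM can be setup remotely and mailed to the participant for use for 7 days at home". If the data are unusable or the device is damaged, "the participant may be asked to wear an alternate SAM device for another 7 consecutive days".

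**Limit on the baseline week.** The monitor records "steps taken over 7-days between the assessment period (after consent), but before the initiation of the intervention". The week must therefore precede treatment, but nothing says it must precede knowledge of the arm. The SAP (Intervention overview) places the first therapy visits in weeks 2 and 3 after the baseline assessment.

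**Use of the week.** SAP sections 4 and 6 define both primary outcomes as changes from this week to one year, compared by an unadjusted Satterthwaite t-test.

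**The concern.** Disclosure takes 0 to 2 business days and wear takes 7 days, and both run from the same session. A plan followed as written therefore lets part or all of the baseline be recorded by people who know their arm. Because treatment has not begun and the monitor shows no step counts to the wearer, the risk is a behavioural reaction to the assignment, not an early treatment effect. The outcome is voluntary walking, and the Protocol already withholds monitor feedback because measured behaviour can be influenced.

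Randomisation balances what precedes disclosure. It cannot balance a reaction that follows it. If the arms react differently, the difference enters the change score with its sign reversed. More baseline walking in the mHealth arm would mask a benefit, and more in the control arm would exaggerate one. Knowledge of the arm cannot be avoided at 12 months, but it can be avoided at baseline.

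**Working it through.** **1. Days after disclosure.** The inputs are a lag of 0, 1 or 2 business days and 7 days of wear (Protocol). I assume a Monday-Friday visit, no holiday, and wear starting at the visit. Days after disclosure = 7 − calendar days elapsed to disclosure.

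| Told | Mon | Tue | Wed | Thu | Fri |
|---|---|---|---|---|---|
| At the visit | 7 | 7 | 7 | 7 | 7 |
| +1 business day | 6 | 6 | 6 | 6 | 4 |
| +2 business days | 5 | 5 | 5 | 3 | 3 |

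The range is 3 to 7 in 24-hour days. Counting only full calendar days after the disclosure day, with the visit as day 1, gives 2 to 6. A holiday on the following Monday lowers the minimum in the table to 2. If wear starts d days before the session (for example at an earlier remote part), each count falls by d: d = 3 gives 0 to 4, and d = 7 gives 0. A mailed device that starts after disclosure gives 7.

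**2. Shift in the contrast.** Bias = f × s, where s is the between-arm difference in reaction (steps/day) and f the fraction of the week affected. The values of s are arbitrary; f runs from 3/7 to 1.
- s = 50: 50 × 3/7 = 21 to 50 steps/day, or 5% to 12% of the planned 432.
- s = 100: 100 × 3/7 = 43 to 100 steps/day, or 10% to 23% of 432.

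**3. The SAP's own basis.** The SAP uses a difference of 432, SDs of 1046 and 560, and 61 per arm. SE = √((1046² + 560²)/61) = 151.9, Satterthwaite df = 91.8, and noncentral-t power = 0.8034, which reproduces the SAP's 0.80342. With a masking bias, power is evaluated at 432 − f × s:
- s = 50: power 0.76 to 0.70. False-positive rate with no true effect: 0.052 to 0.062.
- s = 100: power 0.72 to 0.58. False-positive rate: 0.059 to 0.100.

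**4. Sensitivity to the SD.** The SDs of 1046 and 560 are the pilot's baseline SDs, used as SDs of change. As an alternative, SD of change = √(a² + b² − 2rab), with (a, b) = (1046, 1900) for mHealth and (560, 1636) for control, and an assumed within-person correlation r of 0.3 to 0.7.
- r = 0.3: SDs 1874 and 1562, SE 312, power 0.28.
- r = 0.7: SDs 1386 and 1307, SE 244, power 0.42.
- Further power lost to a masking bias: 0.02 to 0.08 at s = 50, and 0.04 to 0.15 at s = 100.
- False-positive rate: 0.051 to 0.055 at s = 50, and 0.052 to 0.069 at s = 100.

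The low starting power here is a separate sample-size matter and is not caused by disclosure. Only the losses bear on this point.

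**5. Moderate-intensity minutes.** The same route applies, but the documents give no figures from which to size it.

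**The case against.** The consequence is conjectural. Nothing in the documents shows that steps change after disclosure, a reaction common to both arms cancels, and both arms are told to walk and exercise at the same frequency on the same visit schedule. The cruder contaminants are already handled, since wear precedes treatment and the monitor is silent. This stands, and it is why the effect is called probably small and s is labelled arbitrary.

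The 3-to-7 count depends on conditions the documents do not fix, namely visit weekday, holidays and start of wear. That also stands, and across all permitted routes the range is 0 to 7. Disclosure before the week ends remains the ordinary result of the plan when wear starts at the visit.

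The remedy may come late. The Protocol's qualitative section refers to 12-month assessments due between 1 September and 31 December 2023. If those were the last, enrolment ended around the end of 2022. This is suggestive only, as the dates may mark just the interview window.

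Waiting for a mailed device might seem to collide with a week-2 first visit. It adds no delay, because the Protocol already requires baseline wear before the intervention starts. What shrinks is the notice of the arm.

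Coordinator instructions and the monitor handout are not among the documents, so actual practice may be better than the written plan.

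**Conclusion.** The point holds. As written, the plan allows the baseline week of both primary outcomes to be recorded partly or wholly after participants know their arm: 3 to 7 of 7 days if wear starts at a Monday-Friday visit with no holiday. Confidence is high on the sequence. The consequence is of unknown size and direction and is probably small. A between-arm reaction of 50 to 100 steps/day would move the steps contrast by 21 to 100 against 432, but those values of s are illustrations, not estimates. It is an avoidable weakness that should be corrected because correction is cheap. It does not by itself invalidate the primary comparison.

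**What to change.** **Participants still to be enrolled**
- Amend Protocol, Assessment Procedures, so that the arm is disclosed, and preferably the REDCap randomisation performed, only after the 7-day baseline wear has ended. Align the SAP's randomisation paragraph and the coordinator instructions.
- Book the first therapy visit without naming the arm, which the shared visit schedule permits.
- State when baseline wear starts if the baseline is split into remote and in-person parts or the device is mailed.
- Flag any baseline re-wear that follows disclosure instead of delaying the participant.

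**Participants already enrolled**
- Tabulate disclosure timing relative to baseline wear where dates exist. The start of wear should be recoverable: "Study personnel will log pertinent setup information (start time, height, weight etc) on the SAM Setup form".
- Add a supportive comparison of 12-month monitor values that does not use the monitor baseline. On the pilot's 12-month SDs, SE = √((1900² + 1636²)/61) = 321 steps/day, against 312 to 244 for the change score at r = 0.3 to 0.7. The ratios are 321/312 = 1.03 and 321/244 = 1.32, so its SE is 3% to 32% larger.

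**Cost.** One Protocol sentence, a matching SAP line and coordinator instruction, one table and one supportive analysis. Arm-specific preparation material goes out later, with at most about a week's notice if the SAP's week-2 first visit still applies, and less if a mailed device starts late. If enrolment has closed, only the table and the supportive analysis remain.

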COVER PAGE

Statistical Analysis Plan

Official Title: Walking and mHealth to Increase Participation in Parkinson Disease

NCT Number: NCT03517371

Document Date: August 20, 2019

Walking and mHealth to Increase Participation in Parkinson Disease (WHIP-PD)

STATISTICAL ANALYSIS PLAN

Authors:

[name], Director of the Program of Physical Therapy, Professor of Physical Therapy, Neurology, and Neuroscience, Washington University School of Medicine

[name], Director of the Center for Neurorehabilitation, Assistant Professor of Physical Therapy & Athletic Training, Programs in Physical Therapy, Boston University

[name], Senior Scientist, Program in Physical Therapy, Washington University School of Medicine

Date: August 20, 2019

Version: 3

INTRODUCTION

Design

This is a two-arm, single-blinded, 1-year randomized controlled trial (RCT). Persons with mild to moderate Parkinson disease (PD) are randomly assigned to one of two treatment arms (mHealth or active exercise control). Two sites are participating in this RCT: Boston University (BU) and Washington University (WU) School of Medicine.

Intervention overview

Participants in the ***mHealth*** condition participate in a cognitive-behavioral community-based walking program plus home-based walking enhancing progressive resistance exercises delivered using a mobile health platform. Specifically, the program will employ a “Connected Behavioral Approach” to target self-efficacy by identifying maladaptive thoughts, providing feedback to reinforce desired behavior, promoting goal setting and action planning, and offering tailored instruction via a mobile health technology that connects participants to a physical therapist.

In this treatment arm, participants will attend a total of eight, 1-1.5 hour, in-person visits with a trained physical therapist in the clinic at BU or WU. Six of the eight visits will be spread out over the first three months (one visit the 2nd and 3rd week after baseline assessment; then bi-weekly) of the 12-month intervention period to optimize uptake of the walking program and walking enhancing exercises. Remote interaction using the mHealth platform will also occur during this 3-month period. Early visits will also ensure that each participant is able to successfully use the technology. The remaining two physical therapist sessions will be “booster” visits occurring at 3-month and 6-month to review goals, address barriers to exercise, and discuss strategies for relapse prevention. During the final 6 months (months 7-12), no interactions (in person or remote) will occur between the physical therapist and participants; however, participants will continue to use the mHealth application to support continued successful engagement in the exercise program.

Participants will be able to contact the physical therapist through the app during months 7-12 if needed; however, planned interactions will not be scheduled.

Participants in the ***active exercise control condition*** receive the same components and dose of walking and exercise but without a cognitive-behavioral approach or the use of mobile health technology. Participants in the control group have eight in-person visits with the intervention physical therapist over 12-months. Six visits occur in the first three months with follow-up booster visits at 3 and 6 months – equivalent to the dose provided to the mHealth condition. Participants are instructed by the physical therapist to engage in walking and perform the same progressive resistance exercises (tailored to their needs and provided in written format) at the same frequency (5x/week) as participants in the mHealth condition. Participants in the active control condition will also be instructed to gradually progress their exercise program and to increase the amount of walking over a 1-year period. No cognitive-behavioral approaches or mHealth technology will be provided.

STATISTICAL ANALYSIS PLAN – WHIP-PD

1 ANALYSIS OBJECTIVES

Hypotheses/Aims

Aim 1: Determine if “Connected Behavioral Approach” is more effective than an active exercise control in increasing real-world walking activity in persons with PD.

Hypothesis 1: Participants in the mHealth arm will have greater change in (1a) daily steps (Step Activity Monitor (SAM) worn in the free-living environment) and (1b) moderate intensity minutes (number of minutes in which participants walk greater than 100 steps per minute per day) between baseline and 12-months compared to the active exercise control condition.

Aim 2: Determine if our “Connected Behavioral Approach” is more effective than an active exercise control condition in improving walking capacity in persons with PD.

Hypothesis 2: Participants in the mHealth arm will have greater change in walking capacity (6-min walk test, 10-meter walk test) between baseline and 12 months compared to the active exercise control arm.

2 ANALYSIS SETS/POPULATIONS/SUBGROUPS

Sample size

Steps per day via SAM: In our pilot study, low activity participants in the mHealth group had 6028 (SD 1046) steps per day at baseline and 6918 (1900) at 12 months. Participants in the active control group had 6330 (SD 560) steps per day at baseline and 6788 (SD 1636) at 12 months.¹ Using the Two-Sample T-Test Allowing Unequal Variance Procedure in PASS Power Analysis and Sample Size software, group sample sizes of 61 participants per group will be needed to achieve 80% power, $\alpha = .05$. To account for 20% drop out rate, 74 participants will need to be recruited per group for a total of 148 participants.

Two-Sample T-Tests Allowing Unequal Variance

Numeric Results for an Unequal-Variance T-Test

$$\delta = \mu_1 - \mu_2$$

$$\text{Hypotheses: } H_0: \delta \neq 0 \text{ vs. } H_1: \delta \neq 0$$

Target Power	Actual Power	N1	N2	N	μ_1	μ_2	δ	σ_1	σ_2	Alpha
0.80	0.80342	61	61	122	890.0	458.0	432.0	1046.0	560.0	0.050

Moderate Intensity Minutes (# of minutes in which >100 steps were accumulated): We will have sufficient power to detect differences in number of minutes of moderate intensity steps collected over 7 days via the SAM. With 74 participants per group we will have 86%

STATISTICAL ANALYSIS PLAN – WHIP-PD

power to detect an effect size of 0.5 in number of minutes of moderate intensity steps collected over 7 days via the SAM.

Two-Sample T-Tests using Effect Size

Numeric Results for Two-Sample T-Test

Alternative Hypothesis: H1: $d \neq 0$

Power	N1	N2	N	d	Effect Size	Alpha
0.2270	74	74	148	0.20	0.050	
0.8557	74	74	148	0.50	0.050	
0.9980	74	74	148	0.80	0.050	

Randomization and relevant demographics

Block randomization (to keep randomization equal throughout the study) of participants to the two treatment arms by site using Data Access Groups will be completed using the REDCap Randomization Model. Participants will also be randomized by gender and Hoehn & Yahr. The study coordinator will click a randomize button in the REDCap database for their site after confirming eligibility and obtaining consent.

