4 ENDPOINTS AND COVARIATES

Endpoints

The primary outcomes are the change from baseline to one year in mean number of steps per day over a seven-day period (via SAM) and the number of moderate intensity minutes (number of minutes with greater than 100 steps) for the mHealth compared to active exercise control participants.

Secondary outcome is the change from baseline to one year in walking capacity. Walking capacity will be the number of meters walked during the 6MWT and meters per second for the 10MWT.

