5 HANDLING OF MISSING VALUES OR OTHER DATA CONVENTIONS

Missing data

Vigorous attempts will be made to obtain follow-up assessments on all participants, regardless of compliance with treatment protocols. If a participant cannot complete any of the follow-up assessments, the reason will be clearly documented.

Non-normal data

Distributions will be examined to determine the need for data transformation, winsorizing, or nonparametric analyses.

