6 STATISTICAL PROCEDURES

Primary Outcome Analyses

Our primary aim is to determine effectiveness of the intervention to improve walking behavior at one year. We will conduct the main analyses on the full sample and compare SAM data for change from baseline to one year in (1a) mean number of steps per day and (1b) number of minutes in which participants walk greater than 100 steps per minute per day (moderate intensity minutes) over a seven-day period for the mHealth versus active exercise control participants.

STATISTICAL ANALYSIS PLAN – WHIP-PD

The unadjusted treatment comparison will be determined using a Satterthwaite unpooled t-test to allow for unequal variance in treatment groups.

The two-sided 0.05 level will be used for significance in all analyses.

Secondary Outcome Analyses

We will use a similar approach to the analysis described above to analyze the effect of the intervention on secondary outcomes of walking capacity (6MWT and 10MWT).

Each hypothesis will be tested two-sided (level of significance of 0.05).

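### The steps power calculation uses the pilot's baseline SDs as SDs of 12-month change; if both pilot SDs describe the same participants, power at 61 completers per arm is at most 68%, not 80%

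*SAP*

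**What the plan says.** SAP Section 2 (Sample size) bases the steps calculation on the pilot: "low activity participants in the mHealth group had 6028 (SD 1046) steps per day at baseline and 6918 (1900) at 12 months". For control: "Participants in the active control group had 6330 (SD 560) steps per day at baseline and 6788 (SD 1636) at 12 months". The power table below this enters means of 890 and 458, a difference of 432, SDs of 1046 and 560, and two-sided alpha 0.05. It reports power of 0.80342 with 61 per arm, and the text concludes that "group sample sizes of 61 participants per group will be needed to achieve 80% power".

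On attrition the section says: "To account for 20% drop out rate, 74 participants will need to be recruited per group for a total of 148 participants". For moderate-intensity minutes it says "With 74 participants per group we will have 86" per cent power, at an effect size of 0.5.

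SAP Section 4 defines the endpoint: "The primary outcomes are the change from baseline to one year in mean number of steps per day". SAP Section 6 gives the test: "The unadjusted treatment comparison will be determined using a Satterthwaite unpooled t-test to allow for unequal variance in treatment groups". On missing follow-up, SAP Section 5 commits to vigorous attempts to obtain assessments and adds: "If a participant cannot complete any of the follow-up assessments, the reason will be clearly documented". It names no analysis method for missing 12-month values.

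**The concern.** The means in the power table are changes (6918 − 6028 = 890; 6788 − 6330 = 458), but the SDs beside them match the two baseline SDs exactly. An unadjusted t-test on change has a standard error built from the SD of change. The baseline SD is a different quantity, and the SAP gives no reason to treat the two as equal. It reports neither an SD of change nor a baseline to 12-month correlation.

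The pilot's 12-month SDs are far larger than its baseline SDs (1900 against 1046; 1636 against 560). A spread that grows this much forces a large SD of change whatever the correlation.

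The 80% figure is the stated basis for recruiting 148. If it is too high, a null result would be read as coming from a trial with 80% power for 432 steps/day when it did not have that power. The minutes figure has a related weakness: it counts all 74 recruits per arm, although the same section plans for 20% loss.

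**Working it through.** **Inputs.** From SAP Section 2: pilot means and SDs, difference 432, n = 61 and 74 per arm, 20% drop-out. From SAP Section 6: two-sided alpha 0.05 and the Satterthwaite unequal-variance t-test. The correlation r between baseline and 12 months is not in the documents, so it is varied up to its maximum of 1.

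**1. Reproduce the plan's figure.** Standard error = √[(σ₁² + σ₂²)/n] = √[(1046² + 560²)/61] = 151.9. Noncentrality = 432/151.9 = 2.84, with Satterthwaite df 91.8. Noncentral-t power is 0.8034, matching 0.80342, and 61 is the smallest n that reaches 80%. This confirms that the baseline SDs were the inputs.

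**2. Could 1046 and 560 be SDs of change?** For the same participants, SD of change = √(SD₀² + SD₁₂² − 2·r·SD₀·SD₁₂). Setting this equal to SD₀ gives r = SD₁₂/(2·SD₀).
- mHealth: 1900/(2 × 1046) = 0.91, which is possible but high.
- Control: 1636/(2 × 560) = 1.46, which is impossible.

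**3. Best case.** The SD of change is smallest at r = 1, where it equals |SD₁₂ − SD₀|.
- mHealth: 1900 − 1046 = 854.
- Control: 1636 − 560 = 1076.

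At 61 per arm the standard error is √[(854² + 1076²)/61] = 175.9, the noncentrality is 432/175.9 = 2.46, and power is 68.3%. Each arm is at its own minimum, so this ceiling needs no common r.

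**4. Completers.** 74 × 0.8 = 59.2, so about 59 per arm remain after the planned loss. Power for 432 steps/day, and the difference detectable with 80% power at 59 per arm:

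| r (assumed) | SD of change, mHealth / control | 59 per arm | 61 per arm | 74 per arm | Detectable difference (59 per arm) |
|---|---|---|---|---|---|
| 1 (ceiling) | 854 / 1076 | 66.8% | 68.3% | 76.6% | about 505 |
| 0.9 | 1062 / 1158 | 55% | 57% | 65% | about 580 |
| 0.8 | 1235 / 1235 | 47% | 48% | 56% | about 640 |
| 0.7 | 1386 / 1307 | 41% | 42% | 49% | about 700 |
| 0.5 | 1648 / 1440 | 32% | 33% | 39% | about 805 |

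Only the first row is a bound. The others are illustrations with a common r in both arms. At the bound, 80% power needs 81 completers per arm, more than the 74 recruited.

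**5. Moderate-intensity minutes.** A two-sample t-test at d = 0.5 gives 0.8557 with 74 per arm, matching the SAP. With 59 per arm it gives 76.8%. For 80% at 59 per arm, d must be 0.52.

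**6. Drop-out allowance.** 61 × 1.2 = 73.2, rounded up to 74. That covers 1 − 61/74 = 17.6% loss; a 20% allowance would be 61/0.8 = 76.25, so 77 per arm. This is minor: on the SAP's own SDs, 59 rather than 61 completers gives 79.0% rather than 80.3%.

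**The case against.** The strongest objection is that the 68% ceiling is conditional. The SAP gives no pilot n or attrition, and the mHealth figures are described as those of low-activity participants. If different people contribute to the baseline and 12-month SDs, |SD₁₂ − SD₀| is no longer a strict lower limit. This stands, and the ceiling must carry the condition.

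How far would the condition have to fail? Restoring the entered 560 would need a control 12-month SD, among the same people, of 1120 or less (560 + 560). Restoring 80% power needs less, because both arms' variances count. With mHealth at 854 and r = 1 in both arms, the control 12-month SD would have to be about 1395 or less at 61 completers, or about 1563 at 74, against the quoted 1636. The 76.6% for full completion is therefore sensitive to a small mismatch; the result at planned completion is less so. Both rescues require perfect correlation, and neither makes a baseline SD the right input.

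A baseline-adjusted analysis would have a different residual SD, and the bound does not cover it. With residual SD taken as SD₁₂·√(1 − r²), 61 per arm and a difference of 432, power would be about 46% at r = 0.7 and 86% at r = 0.9. The SAP specifies the unadjusted test, so this does not support its figure.

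The 86% for minutes is correctly computed for 74 per arm, and d = 0.5 is not a pilot estimate. That is fair: the fault there is only that planned attrition is left out.

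Finally, wrong power does not bias the estimate or inflate type I error, a null result should be read from its confidence interval, and the protocol's 2023 dates suggest that n can hardly change now. These points argue against changing the sample size. They do not justify leaving a figure that the pilot data do not support.

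**Conclusion.** The concern holds. The SDs entered for steps are those of the wrong quantity; this is plain from SAP Section 2 and needs no assumption. The size of the error rests on one assumption, that each arm's pilot baseline and 12-month SDs describe essentially the same participants. Given that, planned power for 432 steps/day is overstated by at least 12 percentage points at 61 completers (80.3% against at most 68.3%) and falls to at most 66.8% at the completion the SAP itself plans for. Any correlation below 1 lowers it further. Power for moderate-intensity minutes at d = 0.5 is overstated by about 9 points once planned drop-out is counted (85.6% against 76.8%). Endpoint, test and alpha are unaffected.

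**What to change.** Keep n = 148 and correct SAP Section 2:

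1. Replace 1046 and 560 with the SD of 12-month change in each arm, from the pilot's participant-level data. If these are not available, show power over a range of r and label r as an assumption.
2. Restate steps power for 432 steps/day, or the detectable difference, at about 59 completers per arm.
3. Restate power for moderate-intensity minutes as about 77% at d = 0.5 with 59 completers per arm.
4. State that 74 per arm covers 17.6% drop-out if 61 completers are wanted.

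The cost is SAP wording only, with no extra participants. The downside is that the stated power becomes less favourable for both primary outcomes.

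### Under the SAP's own 20% dropout, 74 per arm leaves 59 rather than 61, and power for moderate-intensity minutes is about 77%, not the stated 86%

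*SAP*

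**What the plan says.** All the figures are in SAP section 2, under Sample size. For steps per day, "group sample sizes of 61 participants per group will be needed to achieve 80% power", and the accompanying table gives an actual power of 0.80342 at 61 per arm. The allowance for attrition follows: "To account for 20% drop out rate, 74 participants will need to be recruited per group for a total of 148 participants".

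The next paragraph covers moderate-intensity minutes: "With 74 participants per group we will have 86"% "power to detect an effect size of 0.5 in number of minutes of moderate intensity steps". Its table enters 74 per arm (148 in total) and lists power of 0.2270, 0.8557 and 0.9980 at standardised effects of 0.2, 0.5 and 0.8. The text describes this power as sufficient.

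SAP section 4 makes both measures primary outcomes, each a change from baseline to one year. For the analysis, section 6 says: "The unadjusted treatment comparison will be determined using a Satterthwaite unpooled t-test to allow for unequal variance in treatment groups". Section 5 commits to energetic follow-up and to recording reasons for missed assessments, but gives no imputation or model-based method for missing 12-month values.

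**The concern.** There are two separate slips, and both concern which n is used. The power formulas themselves are applied correctly.

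First, 74 is too few to leave 61 after a 20% loss. Attrition should be allowed for by dividing by the retained fraction. The printed 74 is what multiplying by 1.2 and rounding up would give.

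Second, steps per day is powered on completers and minutes on recruits. Both outcomes are taken from the same device, worn by the same people in the same week, so someone without a 12-month recording drops out of both comparisons. If 20% loss is the planning assumption for one, it is the planning assumption for the other.

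What is at stake is how the second primary outcome is read. Anyone interpreting a null result on minutes would take the type II error risk at an effect of 0.5 to be about 14% (1 - 0.856). Under the SAP's own assumptions it is about 23% (1 - 0.768).

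**Working it through.** **Inputs**
- Significance level: "The two-sided 0.05 level will be used for significance in all analyses" (SAP section 6).
- mHealth arm: the pilot group "had 6028 (SD 1046) steps per day at baseline and 6918 (1900) at 12 months", so the change is 6918 - 6028 = 890. The SAP's table uses an SD of 1046.
- Control arm: the pilot group "had 6330 (SD 560) steps per day at baseline and 6788 (SD 1636) at 12 months", so the change is 6788 - 6330 = 458. The table uses an SD of 560.
- Difference in change: 890 - 458 = 432 steps per day.
- Minutes: standardised effect d = 0.5.
- Dropout 20%; 74 recruited per arm (SAP section 2).

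**Step 1. Reproduce the SAP's figures**

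For steps per day with n per arm, the unequal-variance t-test has
- SE = sqrt[(1046² + 560²)/n] = sqrt(1,407,716/n)
- Satterthwaite df = (n - 1)(1046² + 560²)²/(1046⁴ + 560⁴) = 1.5297(n - 1)
- noncentrality = 432/SE

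At n = 61: SE = 151.91, df = 91.8, noncentrality = 2.844. Noncentral-t power is 0.80342, an exact match.

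For minutes, the equal-variance t-test has noncentrality d·sqrt(n/2) and df = 2n - 2. At n = 74 and d = 0.5: noncentrality = 0.5 × sqrt(37) = 3.041, df = 146, power 0.8557, again exact. The table's 0.2270 and 0.9980 for d = 0.2 and 0.8 also reproduce.

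**Step 2. Check the attrition allowance**
- Dividing by the retained fraction: 61/(1 - 0.20) = 76.25, so 77 per arm, 154 in total.
- Multiplying: 61 × 1.20 = 73.2, so 74. This matches the SAP.
- Completers from 74: 74 × 0.80 = 59.2, about 59 per arm.
- Loss that 74 can absorb while keeping 61: 1 - 61/74 = 17.6%.

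**Step 3. Recompute power at the n that remains**

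At n = 59, steps per day has SE = 154.47, df = 88.7 and noncentrality 2.797. Minutes at d = 0.5 has noncentrality 0.5 × sqrt(29.5) = 2.716 and df = 116.

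| Outcome | SAP: n per arm, power | Power at 59 per arm |
|---|---|---|
| Steps per day, difference 432 | 61, 80.3% | 79.0% |
| Minutes, d = 0.5 | 74, 85.6% | 76.8% |
| Minutes, d = 0.2 | 74, 22.7% | 19.0% |
| Minutes, d = 0.8 | 74, 99.8% | 99.1% |

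**Step 4. Would correcting the allowance alone be enough?**

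No. Recruiting 77 to retain 61 gives 78.2% power for minutes at d = 0.5. Reaching 80% there takes 64 evaluable per arm (63 gives 79.5%, 64 gives 80.2%). From 74 recruits that allows a loss of only 1 - 64/74 = 13.5%. With 59 per arm, 80% power needs d of about 0.52, and the stated 86% needs d of about 0.56.

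**The case against.** The best defence is about weight. The 74-versus-77 discrepancy costs 1.3 points of power on steps per day. That is less than the uncertainty in the inputs: the SDs used for the change (1046 and 560) are the pilot's baseline SDs, so distinguishing 59 from 61 implies more precision than the calculation has. This stands, and the first slip taken alone is minor.

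For minutes, the SAP discloses that it used 74 per arm, and 85.6% is correct for that n. The 80% target is stated only for steps per day. The effect of 0.5 has no pilot or clinical basis in the document, and moving it to 0.52 restores 80%. These points also stand, so crossing the 80% line should not be made much of. They do not rescue the claim. Whatever threshold is preferred, the figure is nine points too high under the dropout assumed in the preceding paragraph, and it is offered as evidence of sufficient power.

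The SAP prints no inflation formula, so the multiplication by 1.2 is an inference from the result. The shortfall does not depend on it, because 74 × 0.80 is 59.2 however 74 was reached.

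The plan also takes steps against missing data: follow-up regardless of compliance (SAP section 5), and mailed monitors and repeat wear when a recording is unusable (protocol, Primary Outcome Measure). These may keep actual loss below 20%, but the SAP takes no credit for that. Section 6 says the main analyses use the full sample, yet with no method for missing outcomes a t-test on change cannot include people who have no 12-month value.

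**Conclusion.** The concern holds. Under the SAP's own 20% dropout, neither stated power is delivered: steps per day has 79.0% rather than 80.3%, and moderate-intensity minutes at d = 0.5 has 76.8% rather than 85.6%. The correction for minutes carries nearly all the weight, and the steps shortfall is negligible in practice.

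The result assumes equal 20% loss in both arms and analysis of participants with a 12-month value. The steps figure also takes the SAP's SDs for change at face value. The test, the endpoints and the significance level are unaffected; what is wrong is the power the plan reports.

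**What to change.** Keep the target of 148 and correct the sample-size text in SAP section 2:

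- State that 20% dropout from 74 leaves about 59 evaluable per arm, and that 74 preserves 61 only if dropout is at most 17.6%. Note that full cover for 20% would have been 61/0.80, or 77 per arm, so that 74 is not presented as meeting it.
- Give power at 59 per arm for both primary outcomes: about 79% for steps per day and about 77% for minutes at d = 0.5.
- Recompute the minutes table at the evaluable n (19.0%, 76.8% and 99.1% for d = 0.2, 0.5 and 0.8), and remove or qualify the statement that power is sufficient.

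The cost is wording only, with no extra participants and no change to the analysis. The visible consequence is that stated power for the second primary outcome falls from 86% to about 77%. Raising recruitment to 77 per arm would not avoid this, since 61 completers give 78.2% for minutes.
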